10. DRUG INFORMATION

10.1 Liposomal Irinotecan (nal-IRI)

Please refer to the current version of the Investigator's Brochure (IB) for additional information regarding this drug.

The irinotecan liposome injection drug product contains the drug substance irinotecan in the amount equivalent to 5 mg/mL of irinotecan hydrochloride trihydrate. The drug product liposome is a small unilamellar lipid bilayer vesicle, approximately 110 nm in diameter, that encapsulates an aqueous space which contains irinotecan in a gelated or precipitated state, as the sucrosofate salt. The liposome carriers are composed of 1,2-distearoyl-sn-glycero-3-phosphocholine (DSPC), 6.81 mg/mL; cholesterol, 2.22 mg/mL; and methoxy-terminated polyethylene glycol (MW 2000)-distearoylphosphatidylethanolamine (MPEG-2000-DSPE), 0.12

mg/mL. Each mL also contains 2-[4-(2-hydroxyethyl) piperazin-1-yl] ethanesulfonic acid (HEPES) as a buffer, 4.05 mg/mL; sodium chloride as isotonicity reagent, 8.42 mg/mL; and sucrose octasulfate as the drug trapping agent, 0.9 mg/mL. The solution is buffered at pH 7.25. In the vialed product, greater than 98% of the drug is encapsulated in the liposome carrier. Irinotecan liposome injection is supplied as a sterile solution containing 4.3 mg/ml of irinotecan free base encapsulated in liposomes. The appearance of irinotecan liposome injection is white to slightly yellow opaque liquid.

10.1.1 Supplier/How Supplied

Ipsen Biopharmaceuticals will supply Irinotecan liposome injection at no charge to subjects participating in this clinical trial.

The investigator shall take responsibility for and shall take all steps to maintain appropriate records and ensure appropriate supply, storage, handling, distribution, and usage of investigational product in accordance with the protocol and any applicable laws and regulations.

10.1.2 Preparation

Irinotecan liposome injection is supplied as a sterile solution containing 4.3 mg/ml of irinotecan on the free base basis (equivalent to 5.0 mg/ml of irinotecan hydrochloride trihydrate) encapsulated in liposomes. Prior to administration, irinotecan liposome injection drug product must be diluted in 5% Dextrose Injection or Normal Saline to a suitable volume for infusion. Irinotecan liposome injection and admixtures of irinotecan liposome injection must not be frozen, as freezing temperature may disrupt the liposome structure in the drug product and lead to the release of free irinotecan.

10.1.3 Storage and Stability

Please see the clinical protocol and product labels for instructions on irinotecan liposome injection storage conditions, shelf life, and product administration. Prior to administration, irinotecan liposome injection must be diluted in 5% Dextrose Injection or Normal Saline (0.9% Sodium Chloride Injection) to a suitable volume for infusion. The solution for infusion (irinotecan liposome injection and its admixtures) must not be frozen. Freezing will disrupt the liposome structure and result in the release of free irinotecan. Because of the potential for microbial contamination during dilution, the solution for infusion should be used immediately, but may be stored at room temperature (15° to 30°C) for up to 4 hours prior to the start of the infusion. If necessary, the solution for infusion may be refrigerated (2° to 8°C) for no more than 24 hours prior to use. Irinotecan liposome injection has been tested for compatibility with limited materials, and no compatibility issues have been identified. The following materials were tested:

- Infusion sets (without in-line filter) made of PVC or polyethylene lined
- IV bags made of PVC or coextruded film of polyolefin/polyamide

Store Irinotecan liposome injection at 2°C to 8°C (36°F to 46°F). Do NOT freeze. Protect from light.

10.1.4 Administration

Irinotecan liposome injection should be infused over 90 minutes ($\pm 10 \text{ min}$) without the use of in-line filters. Premedication with a corticosteroid and an anti-emetic at least 30 minutes prior to

administration of irinotecan liposome injection is recommended to prevent nausea/vomiting and to decrease the risk of infusion reaction.

10.1.5 Handling and Disposal

Irinotecan liposome injection is a cytotoxic drug. Follow applicable special handling and disposal procedures.

10.1.6 Dispensing

Irinotecan liposome injection must be dispensed only from official study sites and to eligible subjects under the supervision of the site investigator. Irinotecan liposome injection should be stored in a secure area according to local regulations. It is the responsibility of the site investigator to ensure that study drug is only dispensed to subjects.

10.1.7 Adverse Events

Please see the current IB for a detailed list of adverse events. Most common related to Irinotecan liposome injection include hair loss, dizziness, hypomagnesemia, hypokalemia, decreased appetite and decreased weight.

10.2 FOLFOX

Please refer to the latest version of the prescribing information for each medication. This information can be found at fda.gov and/or on the manufacturer's website. Commercial supplies of each drug will be used in this study and billed to third party payers or the subject. Qualified personnel who are familiar with procedures that minimize undue exposure to themselves and to the environment should undertake the preparation, handling, and safe disposal of chemotherapeutic agents in a self-contained, protective environment.

10.2.1 Oxaliplatin

Please refer to the package insert for complete product information.

10.2.1.1 Availability

Oxaliplatin is commercially available as an aqueous solution in vials containing 50 mg and 100 mg at a concentration of 5 mg/mL. The vials do not contain any preservative and they are intended for single use.

10.2.1.2 Storage and Stability

Intact vials should be stored at room temperature. Solutions diluted in D5W are stable for 6 hours at room temperature or 24 hours under refrigeration.

10.2.1.3 Preparation

The calculated dose of oxaliplatin should be diluted for infusion with 250 mL to 500 mL D5W. Oxaliplatin should not be diluted with a sodium chloride solution. Needles, syringes, catheters or IV administration sets containing aluminum should not be used with oxaliplatin. As with other platinum compounds, contact with aluminum may result in a black precipitate.

10.2.1.4 Disposal

Discard unused portions of injectable chemotherapeutic agents that do not contain a bacteriostatic agent or are prepared with unpreserved diluents (i.e., Sterile Water for Injection USP or 0.9% Sodium Chloride for Injection USP) within eight hours of vial entry to minimize the risk of bacterial contamination.

10.2.1.5 Administration

Oxaliplatin will be administered by intravenous infusion over 2 hours (or per institutional standards). Infusion time may be prolonged (up to 6 hours) in subjects experiencing pharyngolaryngeal dysesthesia.

Oxaliplatin is unstable in the presence of chloride or alkaline solutions. **Do NOT** mix or administer oxaliplatin with saline or other chloride-containing solutions. **Do NOT** administer other drugs or solutions in the same infusion line. Flush IV lines/catheters with Dextrose 5% in Water both before and after oxaliplatin administration.

10.2.1.6 Toxicity

Please see package insert for detailed information. The most commonly observed oxaliplatin toxicities include neurotoxicity, GI toxicity, and myelosuppression. Three neurotoxicity syndromes have been seen: acute sensory neuropathy develops within hours to 2 days after oxaliplatin administration. Symptoms include paresthesias, dysesthesias, and hypoesthesia of the hands, feet, and perioral region. Jaw spasm, abnormal tongue sensation, dysarthria, eye pain and a sensation of chest pressure have also been noted. Acute sensory neuropathy symptoms may be exacerbated by exposure to cold temperature or cold objects. Symptoms are reversible, usually resolving within 14 days and commonly recurring with further dosing. This syndrome has been observed in about 56% of subjects receiving oxaliplatin with 5-FU and leucovorin.

10.2.2 5-Fluorouracil (5-FU; fluorouracil)

Please refer to the package insert for complete product information.

10.2.2.1 Availability

5-FU is commercially available as a 50 mg/mL solution for injection in 10 mL, 20 mL, 50 mL and 100 mL vials.

10.2.2.2 Preparation

Inspect for precipitate; if found, agitate or gently heat in water bath. These solutions may be prepared in D5W or 0.9% NaCl. 5-FU should not be mixed in the same solution with most parenteral antiemetics.

10.2.2.3 Storage and Stability

Intact vials should be stored at room temperature and protected from light. Slight yellow discolor does not usually indicate decomposition. Stability in ambulatory pumps varies according to the pump, manufacturer of drug, concentration and diluent. Please refer to appropriate reference sources for additional information.

10.2.2.4 Administration

In this study, 5-FU is administered as a IV infusion over 46 hours (or per institutional standards).

10.2.2.5 Toxicity

Nausea, diarrhea, vomiting (mild); stomatitis: 5-8 days after treatment initiation; myelosuppression: granulocytopenia (9-14 days); thrombocytopenia (7-14 days); Alopecia; loss of nails; hyperpigmentation; photosensitivity; maculopapular rash; urticaria; anaphylactoid reaction/anaphylaxis (hypotension, wheezing/stridor); palmar–plantar erythrodysesthesias: (42-82% receiving continuous infusion); CNS effects: cerebral ataxia (rare); cardiotoxicity: Myocardial infarction, angina; asymptomatic S–T changes 68%; ocular effects: excessive lacrimation and less commonly, tear duct stenosis.

10.2.2.6 Drug Interactions

Leucovorin enhances the cytotoxicity of 5-FU by forming a more stable tertiary complex with thymidylate synthase. Concomitant administration of 5-FU with warfarin has been reported to result in increased INR/prolonged prothrombin time. Subjects receiving both drugs should be followed with weekly INRs.

10.2.3 Leucovorin Calcium (Folinic Acid)

Please refer to the package insert for complete product information.

In the case of a leucovorin shortage, levo-leucovorin may be administered (dose to be at site investigator's discretion). Other dosing alternatives may also be used during leucovorin shortage such as leucovorin 200 mg/m^2 .

10.2.3.1 Availability

Leucovorin calcium is commercially available in: 50 mg, 100 mg, 200 mg, 350 mg and 500 mg vials for reconstitution, and as a solution for injection in 50 mL vials at a concentration of 10 mg/mL.

10.2.3.2 Storage and Stability

Intact vials should be stored at room temperature and protected from light. Solutions reconstituted with BWI are stable for at least 7 days at room temperature. Solutions diluted for infusion are stable for 24 hours at room temperature and 4 days under refrigeration.

10.2.3.3 Preparation

Leucovorin may be reconstituted with Bacteriostatic Water for Injection (BWI), Sterile Water For Injection, or bacteriostatic NaCl or NaCl. Solutions should be further diluted in D5W, 0.9% NaCl or Ringers solution for infusion over two hours.

10.2.3.4 Administration

Leucovorin will be administered as an IV infusion over 30 minutes (or per institutional standards).

10.2.3.5 Toxicity

The only adverse reactions associated with leucovorin are allergic reactions. These are extremely uncommon.

11. ADVERSE EVENTS

11.1 Definitions

11.1.1 Adverse Event (AE)

An AE is any untoward medical occurrence whether or not considered related to the study drug that appears to change in intensity during the course of the study. The following are examples of AEs:

- Unintended or unfavorable sign or symptom
- A disease temporally associated with participation in the protocol
- An intercurrent illness or injury that impairs the well-being of the subject

Abnormal laboratory values or diagnostic test results constitute AEs only if they induce clinical signs or symptoms or require treatment or further diagnostic tests. Hospitalization for elective surgery or routine clinical procedures that are not the result of an AE (e.g., surgical insertion of central line) should not be recorded as an AE. Disease progression should not be recorded as an AE, unless it is attributable to the study regimen by the site investigator.

11.1.2 Serious Adverse Event (SAE)

An SAE is an adverse event that:

- Results in death. **NOTE**: Death due to disease progression should not be reported as a SAE, unless it is attributable by the site investigator to the study drug(s)
- Is life-threatening (defined as an event in which the subject was at risk of death at the time of the event; it does not refer to an event which hypothetically might have caused death if it were more severe)
- Requires inpatient hospitalization for >24 hours or prolongation of existing hospitalization. **NOTE:** Hospitalization for anticipated or protocol specified procedures such as administration of chemotherapy, central line insertion, metastasis interventional therapy, resection of primary tumor, or elective surgery, will not be considered serious adverse events.
- Results in persistent or significant disability/incapacity
- Is a congenital anomaly or birth defect
- Is an important medical event (defined as a medical event(s) that may not be immediately life-threatening or result in death or hospitalization but, based upon appropriate medical and scientific judgment, may jeopardize the subject or may require intervention (e.g., medical, surgical) to prevent one of the other serious outcomes listed in the definition above). Examples of such events include, but are not limited to, intensive treatment in an emergency room or at home for allergic bronchospasm; blood dyscrasias or convulsions not resulting in hospitalization; or the development of drug dependency or drug abuse.
- Pregnancy
- Overdose

11.1.3 Unexpected Adverse Event

For this study, an AE is considered unexpected when it varies in nature, intensity or frequency from information provided in the current IB, package insert, or when it is not included in the informed consent document as a potential risk. Unexpected also refers to AEs that are mentioned in the IB as occurring with a class of drugs or are anticipated from the pharmacological properties of the drug, but are not specifically mentioned as occurring with the particular drug under investigation.

11.1.4 Relatedness

AEs will be categorized according to the likelihood that they are related to the study drug(s). Specifically, they will be categorized using the following terms:

Unrelated	The Adverse Event is not related to the drug(s)	
Unlikely	The Adverse Event is doubtfully related to the drug(s)	
Possible	The Adverse Event may be related to the drug(s)	
Probable	The Adverse Event is likely related to the drug(s)	
Definite	The Adverse Event is clearly related to the drug(s)	

11.2 Reporting

11.2.1 Adverse Events

- AEs will be recorded from time of signed informed consent until 30 days after discontinuation of study drug(s) and/or until a new anti-cancer treatment starts, whichever occurs first.
- AEs will be recorded regardless of whether or not they are considered related to the study drug(s).
- All AEs will be recorded in the subject's medical record and on the appropriate study specific eCRF form within the EDC system.
- All AEs considered related to study drug(s) will be followed until resolution to ≤ Grade 1 or baseline, deemed clinically insignificant, and/or until a new anti-cancer treatment starts, whichever occurs first.
- Asymptomatic laboratory abnormalities that do not require treatment will not be collected as adverse events.

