1.3.3.1.1 Safety Data from Ongoing MM-398-07-02-03 Study

A Randomized, Open-label Phase 2 Study of Nanoliposomal Irinotecan (nal-IRI)-containing Regimens versus nab-paclitaxel plus Gemcitabine in Patients with Previously Untreated, Metastatic Pancreatic Adenocarcinoma (NCT02551991)

This study is an open-label, phase II study to assess the safety, dose-limiting toxicities (Part 1A only), tolerability, and preliminary efficacy of irinotecan liposome injection in combination with oxaliplatin+5-FU/LV in subjects with metastatic pancreatic adenocarcinoma who have not received prior systemic anti-tumor therapy. The study comprises an initial dose exploration (Part 1A) followed by dose expansion (Part 1B ongoing in the extension phase) of the irinotecan liposome injection+ oxaliplatin+5-FU/LV regimen.

For the 56 subjects treated, all (100.0%) had treatment-emergent adverse events (TEAEs). There were nine TEAEs that were defined as Dose Limiting Toxicities (DLTs) that were reported by five subjects across the four dose exploration cohorts (diarrhea, n=2; vomiting, anal fissure, anal inflammation, proctalgia, neutropenic infection, neutropenic sepsis, and febrile neutropenia, all n=1), including one subject treated in Part 1A- Cohort B who was included in the pooled analysis (febrile neutropenia)

Treatment-related TEAEs Grade 3 or higher were reported by 41 of 56 subjects, including 22 subjects from the pooled analysis of 32 subjects treated with irinotecan liposome injection 50 mg/m2+LV 400 mg/m2+5-FU 2400 mg/m2 and oxaliplatin 60 mg/m2. The TEAEs included: neutropenia, n=10; febrile neutropenia, hypokalemia, both n=4; diarrhea, nausea, both n=3; anemia, vomiting, both n=2, with no reported Grade 3 or higher fatigue or peripheral neuropathy.

SAEs were reported by 34 of the 56 treated subjects, including 17 of the 32 subjects in the pooled analysis, with 23 subjects reporting treatment-related SAEs. In the pooled analysis, 10 of the 32 subjects had treatment-related SAEs: nausea, febrile neutropenia, both n=3; diarrhea, vomiting, both n=2; colitis, enterocolitis, stomatitis, anemia, pneumonia, and pyrexia, all n=1. At the data cut-off there were no treatment-related TEAEs leading to death.

There were 19 subjects who reported TEAEs leading to discontinuation (including eight subjects in the pooled analysis), with 39 subjects requiring dose adjustment due to AEs (including 26 subjects in the pooled analysis).

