6.2.2 Dose Reduction of Oxaliplatin

- a. If the subject develops persistent grade 2 neurosensory events, the dose of oxaliplatin will be reduced to 48 mg/m^2 for first occurrence, or 36 mg/m^2 for second occurrence.
- b. If the subject develops grade 3 or 4 gastrointestinal toxicities (despite prophylactic treatment) and recovers from them, the dose of oxaliplatin will be reduced to 48 mg/m² for first occurrence, or 36 mg/m² for second occurrence.
- c. If the subject develops grade 4 neutropenia or febrile neutropenia or grade 3/4 thrombocytopenia, the next dose will be delayed until neutrophils 1,500/µL and platelets 75,000//µL. Granulocyte colony-stimulating factor (G-CSF) may be administered as indicated.
- d. If the subject develops persistent grade 3 neurosensory events, discontinue oxaliplatin.

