12.2.2 Definition of Secondary Endpoints

- Objective response rate (ORR) as determined by the proportion of subjects with either complete response or partial response as defined by RECIST 1.1 at 8 weeks, 16 weeks, and 24 weeks following initiation of FOLFOX-nal-IRI.
- Stable disease rate (SDR) as determined by the proportion of subjects with no progression of disease as defined by RECIST 1.1, at 8 weeks, 16 weeks, and 24 weeks following initiation of FOLFOX-nal-IRI.
- Rate of resectability as determined by the proportion of subjects who undergo surgical resection of tumors.
- The serum levels of CA 19-9 prior to initiation of chemotherapy and after every 2 cycles (every 4 weeks) following initiation of FOLFOX-nal-IRI.
- Progression-free survival (PFS) as determined by the time interval from the date of first dose of study drug to first documented disease progression or death from any cause, whichever occurs first, if evaluable.
- Overall survival (OS) as defined as the time interval from the date of the first dose of study drug to date of death from any cause.
- Safety and tolerability of FOLFOX-nal-IRI; Grade 3 and 4 toxicities as defined by the NCI Common Terminology Criteria for Adverse Events (NCI CTCAE) v5.

• Quality of life as measured at baseline and after every 4 cycles (every 8 weeks) using the European Organization for Research and Treatment of Cancer Quality-of-Life Core Questionnaire (EORTC-QLQ-C30).

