12.6.2 Analysis Plans for Secondary Objectives

The Secondary Objectives will be analyzed as described in the section 12.2.2, Definition of Secondary Endpoints.

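### The safety endpoint counts Grade 3 and 4 toxicity, but asymptomatic, untreated laboratory abnormalities are not collected at any grade, so severe neutropenia and thrombocytopenia can be missed

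*Combined protocol and SAP*

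**What the plan says.** The safety endpoint in 2.2.2, repeated in 12.2.2, is safety and tolerability, specified as "Grade 3 and 4 toxicities as defined by the NCI Common Terminology Criteria for Adverse Events (NCI CTCAE) v5". For its analysis, 12.6.2 says only: "The Secondary Objectives will be analyzed as described in the section 12.2.2, Definition of Secondary Endpoints". Section 12.4 adds the evaluable population (at least one dose) and the CTCAE version.

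Two passages decide whether a laboratory result becomes an adverse event:

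- Section 11.1.1: "Abnormal laboratory values or diagnostic test results constitute AEs only if they induce clinical signs or symptoms or require treatment or further diagnostic tests".
- Section 11.2.1: "Asymptomatic laboratory abnormalities that do not require treatment will not be collected as adverse events".

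Section 6.2.2 attaches a dose action to severe counts: "If the subject develops grade 4 neutropenia or febrile neutropenia or grade 3/4 thrombocytopenia, the next dose will be delayed". G-CSF is discretionary (5.4, 6.2.2). The study calendar schedules a CBC (including ANC and platelets) and a CMP at screening, on Day 1 of cycles and at the safety visit. Section 14.2 says that a selection of standard-of-care data goes into the EDC, and it does not name blood counts.

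For an earlier study of the same combination, 1.3.3.1.1 gives Grade 3 or higher treatment-related events, "including 22 subjects from the pooled analysis of 32 subjects" treated at this protocol's four doses, and then lists: "The TEAEs included: neutropenia, n=10; febrile neutropenia, hypokalemia, both n=4; diarrhea, nausea, both n=3".

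**The concern.** The endpoint is defined by grade, but collection depends on symptoms and treatment. The two filters conflict for toxicities that are themselves laboratory findings. Section 1.3.3.1 classes neutropenia that way, naming it with lymphopenia as the commonest Grade 3 or 4 laboratory abnormalities.

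Since 12.4 and 12.6.2 describe no grading from laboratory values, the adverse event record is the only described source for the endpoint. A severe count that causes no symptoms and is left to recover meets the endpoint's grade criterion but fails the collection criterion in 11.2.1. Because G-CSF is discretionary, the same count may be an adverse event at a site that treats it and not at one that waits.

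Tolerability is a stated aim (Sections 5 and 12.1) and part of the hypothesis (1.4). Safety data are weighed at the interim analysis (12.7), and the DSMB reviews an adverse event summary (13.2). The loss can go only one way, towards better apparent tolerability.

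**Working it through.** No figure in the plan needs reproducing here. The check has two parts: tracing severe counts through the rules, and showing how much could be lost.

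**1. Route of a severe count into the endpoint**

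| Case | 11.1.1 | 11.2.1 | In the AE record? |
|---|---|---|---|
| Febrile or symptomatic | AE | not excluded | Yes |
| Asymptomatic, given G-CSF or other treatment | AE | not excluded | Yes |
| Asymptomatic, untreated, further diagnostic tests needed | AE | excluded | Passages conflict |
| Asymptomatic, untreated, next dose delayed | depends on whether repeat counts are further tests or a delay is treatment | depends on whether a delay is treatment | Not stated |
| Asymptomatic, untreated, no further tests, no dose action | not an AE | excluded | No |

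The last row is a real possibility. Grade 3 neutropenia without fever is not among the triggers in 6.2.2, and 6.2.3 holds 5-fluorouracil for Grade 4 myelosuppression.

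**2. Size**

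Inputs:

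- 10 subjects with Grade 3 or higher treatment-related neutropenia (1.3.3.1.1).
- Denominator 32, the pooled cohort that the list follows.
- Target sample size 28 (12.3).
- f, the share of such neutropenia that is asymptomatic and untreated. The documents do not give it, so f is an assumption anywhere from 0 to 100%.

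Rate in the earlier cohort: 10/32 = 31.3%, exact (Clopper-Pearson) 95% CI 16.1% to 50.0%. The next most frequent listed events, febrile neutropenia and hypokalemia, are each 4/32 = 12.5% (3.5% to 29.0%).

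Collected rate = 10/32 × (1 − f). Expected collected count among 28 = 28 × 10/32 × (1 − f).

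| Assumed f | Collected rate | Expected count of 28 |
|---|---|---|
| 0% | 31.3% | 8.75 |
| 25% | 23.4% | 6.56 |
| 50% | 15.6% | 4.38 |
| 75% | 7.8% | 2.19 |

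At f = 0 nothing is lost, and at f = 100% nothing is collected. The calculation treats 31.3% as the full rate before any exclusion, which is itself an assumption because the earlier study's collection rule is not given.

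**The case against.** The strongest reply is that most clinically important neutropenia is still captured. Febrile, symptomatic and treated cases are adverse events under both sections. Section 11.1.1 also admits abnormalities that need further diagnostic tests. The delay in 6.2.2 lasts until counts recover to stated levels, which only repeat counts can show, so a site could reasonably record such a case. Section 6 also has subjects evaluated for adverse events that require drug interruption. The endpoint is secondary and descriptive, and no numerical safety rule hangs on it.

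Much of this stands. It rules out several stronger readings that a reader might infer:

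- *Neutropenia is certain to be under-counted.* The rules allow a loss but do not make one inevitable; with f = 0 there is none.
- *The rate would be halved.* The 50% row is one illustration. The documents support no particular share.
- *The result could not be compared with the earlier cohort.* Section 1.3.3.1.1 does not say how that study collected laboratory abnormalities. Its 10/32 may already reflect a similar exclusion. Comparability is unassured, not disproved, and the protocol plans no formal safety comparison.
- *Fatal toxicity is lost because the endpoint stops at Grade 4.* Section 6 covers adverse events of all grades. Events resulting in death are SAEs (11.1.2), apart from deaths due to progression not attributed to study drug, and SAEs are entered on the eCRF (11.2.2.1). The missing Grade 5 is a gap in wording and has no bearing on the neutropenia count.

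The reply does not remove the gap. Section 11.2.1 has no further-tests limb and no exception by grade, and it is the passage that tells sites what to collect. Scheduled ANC values do not close it either, because nothing says that they are entered in the EDC or used to grade toxicity.

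**Conclusion.** The concern holds in a limited form. As written, an asymptomatic, untreated Grade 3-4 neutropenia or thrombocytopenia can be left out of an endpoint defined as Grade 3 and 4 toxicity, and the resulting bias favours the regimen. The problem affects the most frequent severe event listed at these doses.

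The direction follows from the text; the size does not. It depends on f, on reading 32 as the denominator of the listed events, and on taking the earlier rate as complete. Sections 11.1.1 and 11.2.1 are also not the same rule, and neither says whether a dose delay alone counts as treatment, so sites may record the same count differently. This should be corrected, but it does not touch the primary endpoint or the two-stage decision rule.

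**What to change.** Make one of two changes:

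1. In 12.4, add: *The worst CTCAE v5 grade per subject will be derived for each haematological and chemistry parameter from all scheduled CBC and CMP results captured in the EDC, and tabulated beside the adverse event summary.* Section 14.2 should then name these results among the data to be entered.
2. Exempt Grade 3 or higher laboratory abnormalities from the exclusion in 11.2.1, with the same exemption in 11.1.1 so that the definition does not undo it.

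The first option does not rely on each site's judgement and can be applied to subjects already treated. The second is a short text change but depends on sites recording every such result.

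Whichever is chosen, reconcile 11.1.1 with 11.2.1 on further diagnostic tests, and state whether a dose delay alone makes a laboratory abnormality reportable. This concerns recording only and changes no dose rule.

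Separately, as a minor wording correction, state the endpoint in 2.2.2 and 12.2.2 as *Grade 3 or higher (3-5)*. This also matches how 1.3.3.1.1 reports the earlier cohort.

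No visit or blood draw is added. The cost is some programming and, because 14.2 promises only selected data, possibly new eCRF fields and site entry of counts. The reported severe toxicity rate may also look less favourable.
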